9.2 SECONDARY ENDPOINTS

All secondary variables will be analyzed in an exploratory way, with no adjustment for multiple testing. The secondary endpoints include:

- Improvement in ODI and VASPI at 6 months
- Improvement in ODI, SF-36, and VASPI at 6 and 12 months after treatment
- MRI measurements at 6 and 12 months after treatment
- Adverse Event (AE)/ Serious Adverse Events (SAE) rates after treatment
- Hospitalization rate at 12 months after treatment
- Re-operation rate at 12 months after treatment
- Resource utilization following treatment at 6 and 12 months after treatment
- Changes in laboratory tests

Improvement in ODI, VASPI, and SF-36 will be analyzed similar to the primary endpoint, using the Kruskal-Wallis test to test for an overall difference between the three treatment groups. If the overall test is significant, the Dwass, Steel, Critchlow-Fligner Method will be used to asses all pairwise comparisons.

Adverse event rates, serious adverse events rates, hospitalization rates, and re-operation rate will be summarized by treatment group and compared using the chi-square test of independence or Fisher's exact test, as appropriate.

MRI data will be summarized by treatment group as mean at each timepoint, and mean change from baseline. Analyses will be done focusing on the level treated, but additional analyses will be completed which examine all five levels to see if there are adjacent level effects. Group comparisons will be made using the Krusal-Wallis test. If the overall test is significant, the Dwass, Steel, Critchlow-Fligner Method will be used to assess the pairwise comparisons.

Resource utilization and changes in laboratory tests will be summarized by treatment group.

10 Adverse Events

All adverse events will be coded using the standardized Medical Dictionary for Regulatory Activities (MedDRA) central coding dictionary, version 22.1 or greater.

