6.9 Study Duration

The study duration for all enrolled subjects in this trial is approximately 12.5 months, including a 2-week Screening Phase for enrollment following initiation of consent documentation, 12 months of follow-up after treatment in the Active Phase, and an optional long term follow up period of an additional 24 months. Study enrollment is anticipated to require approximately 3-6 months. Therefore, the total study duration will be approximately 39.5 – 42.5 months. Subjects who have unremitting pain, or worsening conditions and who had been randomized to

CONFIDENTIAL	Clinical Protocol	DATE	P	age
		9Dec2019		1
TITLE: V iable A llograft S upplemented Disc Regeneration in the T reatment of		WRITER	NO.	REV
Patients with Low Back Pain wit	th or without Intervertebral Disc Herniation –	TG, DB, PW	28	6
VAST-001-017				

the conservative group will be evaluated clinically and be given the option to crossover into the allograft supplement group. All randomized subjects will have the option to receive the allograft treatment during the optional long term follow up at 24 months. These subjects will fill out questionnaires at 36 months and have the opportunity to do so over the phone.

This study may be terminated by the sponsor if deemed necessary and documented by an amendment to this protocol. If the study is terminated, the sponsor will support follow-up of those subjects who entered the study as though the study had not been terminated.

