7.1.4 Conservative Treatment Group 3 Months (± 14 days), or VA3

Patients randomized to the conservative arm will be evaluated with VASPI, ODI, SF-36 questionnaires as well as complete all required additional assessments as outlined in Appendix A during the 3 months visit. Patients will be evaluated for deteriorating or improving conditions relative to enrollment. Subjects who have experienced a significant decline in condition defined as a 10% increase in pain by VASPI, or a 9-point increase in ODI will be offered the allograft treatment as a crossover. If the subject does not meet the aforementioned changes in ODI or VASPI, or is considering withdrawal, they may also be offered the allograft treatment by physician discretion if condition has significantly declined. Subjects that crossover do not have to re-consent. The crossover allograft treatment can occur at any time period after the 3-month follow-up visit. To administer the crossover allograft treatment, a new visit will be scheduled and this visit will be considered as the new Active Phase Day 0. In addition to the 3 months follow-up visit assessments, these crossover subjects will receive a MRI and X-ray prior to the allograft treatment. All assessments done at this 3 months follow-up visit will be considered as the new baseline assessments. These crossover subjects will receive follow-up visits at 6 months and 12 months after allograft treatment. Crossover subjects will not be replaced by enrolling new patients in the conservative care treatment group.

7.1.5 Active Phase Month 6 (± 30 days) or VA4:

All randomized subjects will return to the clinic 6 months (± 30 days) subsequent to treatment for all safety and efficacy assessments as outlined in Appendix A. ODI, VASPI, and SF-36 questionnaires will be completed by the subject, and assisted by physician or physician designee. All subjects (excluding conservative care crossover subjects) will be randomized to include MRI at 6-month (MRI or no MRI, ratio 1:1) follow-up in addition to all other assessments. This randomization is performed to assess whether predictability at 6 months indicates performance at 12 months. The conservative care subjects that crossover to the allograft treatment group will all receive an MRI at 6-month follow-up after allograft treatment. All subjects will receive an X-ray at the 6-month follow-up visit. Additionally, a review of resource utilization since the Day 0 visit will be completed.

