	trial to be considered a success.						
	Secondary outcomes will be analyzed in an exploratory way at a two-sided $\alpha=0.05$						
	level without controlling for multiple testing						
	Teres, traiout controlling for multiple tosting.						

3 Study Objectives and Endpoints

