4 SAMPLE SIZE

The primary criteria will be analyzed using Wilcoxon rank-sum-test. Based on Fairbanks, 2000¹, Hudson-Cook, 1989² and Fritz, 2001³ a common standard deviation of $\sigma = 15.5$ score points can be assumed.

Fritz, 2001, calculated a Minimum Clinically Important Difference of 6 score points. Reliability is reported in the literature in the range of 0.75 - 0.91. Worst case, using the standard deviation above results in a measurement error of 7.75 score points. Thus, we assume a clinically relevant difference of 9 score points. Under this assumption, the probability p (x < y) = 0.341 (x, y observations in the groups, respectively). A sample size of 40 in each group will have 80 % power to detect with a probability of 0.341 that an observation in one group is less than an observation in the other group using Wilcoxon rank-sum-test with a 0.05 two sided significance level (calculations were done using nquery 4.0).

Approximately 220 subjects randomized to viable allograft or placebo or control in 3.5:1:1 ratio:

Active Allograft = 140 Placebo = 40 Conservative Care = 40

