6.2 MODIFIED INTENT TO TREAT POPULATION (MITT)

The modified intent-to-treat population (mITT) includes all ITT subjects who underwent treatment and had at least one valid post-treatment assessment of the ODI and VASPI. This mITT population is the primary analysis population for efficacy analyses. Subjects are analyzed under the treatment to which they were randomized.

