10.1 All Adverse Events

A summary of incidence rates of individual AEs by System Organ Class (SOC) and Preferred Term (PT) will be prepared. Because a subject may experience more than one AE, summaries will provide both the number of subjects experiencing at least one event and the number of events. Percentages provided will be the percent of subjects experiencing one or more adverse events.

A listing of all adverse events will be provided which includes subject number, AE number, days since procedure, AE SOC and PT, severity of AE, whether or not the AE is classified as serious (SAE), the relationship to investigational device, relationship to procedure, relationship to other etiology, the action taken, and the outcome.

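### Event rates are compared as crude proportions over unequal observation time, and the SAP does not settle the arm, Day 0 or cut-off for conservative-care crossovers

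*SAP*

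**What the plan says.** **Method.** SAP 9.2: "Adverse event rates, serious adverse events rates, hospitalization rates, and re-operation rate will be summarized by treatment group and compared using the chi-square test". The named alternative is Fisher's test. SAP 10.1 makes the adverse event (AE) figure a share of subjects: "Percentages provided will be the percent of subjects experiencing one or more adverse events". The SAP gives no person-time denominator, censoring rule or data cut for these endpoints.

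**Windows.** In SAP 3.2.2, hospitalisation and re-operation are measured at 12 months after treatment. AE and serious adverse event (SAE) rates are only after treatment, with no end.

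**Follow-up.** Protocol 7.1.4 says of the conservative-care arm: "The crossover allograft treatment can occur at any time period after the 3-month follow-up visit". The injection visit becomes a new Day 0, and "These crossover subjects will receive follow-up visits at 6 months and 12 months after allograft treatment". Protocol 8.5 records AEs from enrolment at Day 0 of the Active Phase. Protocol 6.9 nevertheless says: "The study duration for all enrolled subjects in this trial is approximately 12.5 months, including a 2-week Screening Phase". Protocol 6.10 allows withdrawal at any time.

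**Population and arm.** SAP 6.4 makes the safety population primary for AE analyses, grouped by treatment received. SAP 9 analyses secondary variables, which in 9.2 include these four rates, in mITT and PP. For mITT, SAP 6.2 says: "Subjects are analyzed under the treatment to which they were randomized". SAP 13, in the column stating the new plan, names mITT as primary for both efficacy and safety.

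**Status.** SAP 2: "Secondary outcomes will be analyzed in an exploratory way at a two-sided" 0.05 level, without multiplicity control. Allocation in SAP 4: "Active Allograft = 140 Placebo = 40 Conservative Care = 40".

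**The concern.** A chi-square or Fisher test on the share of subjects with an event compares risk fairly only if the groups are watched for similar lengths of time. Here the design itself makes the times differ. Crossovers, who come only from conservative care, are followed from original Day 0 to the injection and then for 12 more months. SAP 5.2 holds the final analysis until the last subject's 12-month visit after treatment, so the extra months will be in the data. Early leavers stay in the denominator as if observed throughout.

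The plan also does not fix where a crossover's events go. As randomised they belong to conservative care. By treatment received they belong to allograft, or to both if the record is split, and SAP 6.4 does not say what to do with a subject who received conservative care and then allograft. For hospitalisation and re-operation, the SAP does not say which Day 0 starts a crossover's 12 months.

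Safety is half of the stated objective and the SAP specifies formal between-group tests. The same data with no true difference could show conservative care as worse or better than allograft, depending on the section the programmer follows.

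**Working it through.** **1. Observation time.**
- Plan's own figure: 0.5 months screening + 12 = 12.5 months. This reproduces Protocol 6.9 (optional extension aside).
- Other completers: 12 months, visit window +30 days (Protocol 7.1.6): 12 to 12 + 30/30.44 = 12.99 months.
- Crossover completers: the earliest Month 3 visit is 3 months - 14 days = 2.54 months. Adding 12 gives 14.54 months, nominally 15, with no maximum because crossover timing is open-ended. With screening this is 15.04 months, so 12.5 does not describe them.

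**2. Assumptions (not in the documents).** Constant hazard, equal in all arms, so the true difference is zero. 12-month risk r = 30% (10% as a check). Crossover fraction f = 10%, 25% or 50%, at 2.5 months. No leavers at first. Group sizes 140 and 40.

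**3. Formula.** Risk over m months = 1 - (1 - r)^(m/12). For r = 0.30:
- 14.5 months: 1 - 0.7^(14.5/12) = 0.3501
- 2.5 months: 1 - 0.7^(2.5/12) = 0.0716

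**4. Three readings.** Differences are conservative care minus allograft.

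(a) As randomised, whole record in conservative care: f × 0.3501 + (1 - f) × 0.30, against 0.30. At f = 25%: 0.0875 + 0.2250 = 0.3125.

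(b) As treated, whole record moved to allograft. At f = 25%, 10 crossovers: allograft (140 × 0.30 + 10 × 0.3501)/150 = 0.3033, conservative care 0.30.

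(c) As treated, record split at the injection and the crossover counted in both groups: conservative care f × 0.0716 + (1 - f) × 0.30, allograft 0.30. At f = 25%: 0.0179 + 0.2250 = 0.2429.

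| f | (a) | (b) | (c) |
|---|---|---|---|
| 10% | +0.5 points | -0.1 | -2.3 |
| 25% | +1.3 | -0.3 | -5.7 |
| 50% | +2.5 | -0.6 | -11.4 |

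At r = 10%, (a) runs from +0.2 to +1.0 points and (c) from -0.8 to -3.9.

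**5. Early leavers.** Assume 15% leave each group, after a mean of 4.5 months in conservative care and 6 in allograft. The 4.5 reflects that conservative care can enter mITT from its Month 3 questionnaires, while most injected subjects first qualify at Month 6 (Month 1 is for the first 24 randomised only). With r = 0.30 the risks over 4.5 and 6 months are 0.1252 and 0.1633. Allograft is then 0.15 × 0.1633 + 0.85 × 0.30 = 0.2795. As randomised:
- f = 25%: 0.25 × 0.3501 + 0.15 × 0.1252 + 0.60 × 0.30 = 0.2863, difference +0.7 points.
- f = 10%: 0.10 × 0.3501 + 0.15 × 0.1252 + 0.75 × 0.30 = 0.2788, difference -0.1 points.

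**6. Under the fix.** A 12-month estimate from original Day 0, censored at last contact, returns r in every arm. Events per person-month, with crossover time split, return the common hazard. Either way the expected difference is 0.

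**The case against.** A reader might infer that the control arm's rates are inflated and that the error favours allograft. The documents do not support this as a general statement. It follows only from the as-randomised reading. SAP 6.4 names the as-treated safety population as primary for AEs, and there the difference moves toward or into the opposite sign. Early leavers lower the crude rate in whichever arm they leave and can cancel the as-randomised excess.

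A reader might also apply 14.5 months to all four rates. Hospitalisation and re-operation carry a nominal 12-month window, and 12 months from either Day 0 is still 12 months. For these two the defect is an undefined start for crossovers and no censoring of leavers. The open-ended problem belongs to AE and SAE rates.

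The size can also be called small. As randomised, with 10% risk, 50% crossover and injection at Month 3 (15 months in all), the conservative-care rate is 0.5 × 0.10 + 0.5 × 0.1234 = 0.1117. The excess of 0.0117 × 40 is 0.47 of one subject. The exact Fisher rejection probability for 140 against 40 goes from 3.6% to 4.4%. In addition, SAP 10.1 provides event counts and a listing with days since procedure, so AE timing would be partly visible.

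These limits on direction, endpoint and as-randomised size stand. What remains is that the test ignores observation time that the design makes unequal, and that the SAP's sections disagree on the arm. The listing does not repair this: days since procedure has no meaning for conservative-care subjects who are never injected, and a listing does not change the tested proportions.

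**Conclusion.** The concern holds in a limited form. The four rates are compared as crude proportions over unequal observation, and population, arm, starting Day 0 and cut-off are not settled for crossovers. The conflict between SAP 6.4 and SAP 9 with 6.2 stands without section 13, which adds to it. Direction and size of the bias are therefore undetermined from the documents.

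Under the assumptions in steps 2 to 4 the as-randomised distortion is modest. The as-treated split with crossovers in both denominators is the larger risk. All of these figures rest on assumed crossover fraction, crossover timing, event risk and dropout, with constant equal hazards. A crossover who withdraws after the injection may have less than 14.5 months.

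The endpoints are exploratory and cannot change the success rule, which rests on ODI and VASPI at 12 months. The change should still be made, because it is inexpensive and bears on how the safety comparison is read.

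**What to change.** 1. Reconcile SAP 6.4, SAP 9 (with 6.2) and SAP 13 on the population and arm for event endpoints. For each endpoint state the population, the Day 0 and the cut-off.
2. In SAP 9.2, for the randomised comparison, count events only to Month 12 from original Day 0 in every arm. Report hospitalisation and re-operation as 12-month Kaplan-Meier or cumulative-incidence proportions, censored at last contact.
3. For AEs and SAEs, add events per person-month observed to the subject percentages in SAP 10.
4. In the as-treated safety analysis, split crossover person-time at the injection. Report post-injection events separately, timed from the injection.

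The cost is SAP wording, routine programming and slightly more complex tables. Event dates, including hospitalisation and re-operation dates, must be available on the CRF. The CRFs are not among the documents, so this should be confirmed first.

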9 STUDY OBJECTIVES AND ENDPOINTS

9.1 Objective

The primary objective of this study is to evaluate the safety and efficacy of viable allograft transplantation for the treatment of patients with symptomatic disc degeneration and tissue loss. There will be three treatment groups: (1) supplemental viable allograft treatment, (2) placebo (saline) treatment, and (3) conservative care treatment.

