12 RISK / BENEFIT ANALYSIS

Both pre-clinical and early clinical results of *in vitro* generated disc-derived cells transplanted into the intervertebral disc space in lieu of, or subsequent to discectomy are promising, thus raising the need for a standardized, well designed clinical trial. Based on prior results for individual patients treated with the surgical standard of care plus *in vitro* generated disc-derived cells, a reduced rate of degeneration after herniation would be expected with the inclusion of an autologous stem cell transplant. Statistical differences have also been defined for levels adjacent to those treated that were correlated with Oswestry disability and quality of life indices.

No clinical data exist in this patient population receiving a transplant of allogeneic donorderived viable matrix. Therefore, the documented risks are those associated with the procedures.

The risks for this procedure include hematoma, epidural bleedings, infections (from local infections up to spondylodiscitis and/or meningitis), neurological deterioration as serious as lesions of the cauda equina (paraplegia secondary to ascending bleeding or infection), paresis, sensory disturbances, disorder of potency or disorder of sexual sensibility, cerebrospinal fluid fistula, retroperitoneal lesions (large vessels, ureter, intestine), instability of the vertebral column, relapsing herniation, incomplete improvement (paresis, sensory disturbances), bladder or bowel dysfunction and recurrence of complaints, in particular pain.

So far, no additional risks due to the application of autologous *in vitro* generated chondrocyte suspension, or matrix carrier itself have been documented. In more than 700 documented cases of autologous stem cell transplants (mainly applied to the knee) similar to the procedure to be followed in this trial, no immunoreaction to the transplant was registered. Furthermore, no infectious reactions to autologous cell transplants have been reported in the literature so far.

The volume supplement of the intervertebral disc space performed in the application of the cell-suspension, comprises no additional risks as no additional intervention will be done to the patient.

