7 GENERAL ISSUES FOR STATISTICAL ANALYSIS

Data will be presented using descriptive statistics. Categorical data will be presented using frequencies and percent of subjects in each category. Continuous data will be presented using mean, standard deviation, median, minimum, maximum, and sample size.

Results will be generated by treatment group.

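### Safety is in the primary objective, yet AE, SAE, hospitalisation and re-operation rates are compared by an exploratory p-value with no risk difference or confidence interval; for uncommon events that p-value says little

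*SAP*

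**What the plan says.** Protocol 9.1 states: "The primary objective of this study is to evaluate the safety and efficacy of viable allograft transplantation". Protocol 12 says of the product: "No clinical data exist in this patient population receiving a transplant of allogeneic donorderived viable matrix".

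SAP 9.2 lists "Adverse Event (AE)/ Serious Adverse Events (SAE) rates after treatment" among the secondary endpoints, with hospitalisation and re-operation rates. Its method for these rates is one sentence: "re-operation rate will be summarized by treatment group and compared using the chi-square test of independence or Fisher's exact test". On their status it says: "All secondary variables will be analyzed in an exploratory way, with no adjustment for multiple testing". The SAP Summary gives the level for secondary outcomes as a two-sided 0.05.

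The rest of the safety output is descriptive. SAP 7 says: "Categorical data will be presented using frequencies and percent of subjects in each category", with results produced by treatment group. SAP 10.1 to 10.4 add incidence by system organ class and preferred term for all AEs, AEs leading to withdrawal, SAEs and related AEs, plus listings. None of these sections mentions an interval, a difference between arms or a margin. SAP 9.2 does name a pairwise follow-up (Dwass, Steel, Critchlow-Fligner) for ODI, VASPI, SF-36 and MRI, but none for the safety rates.

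Planned arm sizes (SAP 4) are "Active Allograft = 140 Placebo = 40 Conservative Care = 40". SAP 6.4 groups the safety population by treatment received. Protocol 7.1.4 allows conservative-care patients to cross over to allograft after the 3-month visit.

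**The concern.** For a product with no prior clinical data in this population, the useful safety statement is how much excess harm the data still allow. A p-value does not give that, and by-arm percentages give a point difference but not its uncertainty. With 40 patients in each comparator, rare or moderately rare events will usually produce a non-significant test whether or not the allograft adds risk.

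A report saying that SAE or re-operation rates did not differ significantly would then be accurate but easy to misread. A single test across three arms also cannot say whether an excess comes from the product or from the disc injection. Allograft against saline addresses the product. Allograft against conservative care addresses product plus injection.

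**Working it through.** **Plan's own figure.** There is none for safety. The only power statement (Protocol 13.3, SAP 4) concerns a 9-point ODI difference. No event rate, margin or precision target is given, so all rates below are assumptions.

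**Inputs.** Arms of 140, 40 and 40 (SAP 4); two-sided 0.05 without adjustment (SAP 2 and 9.2); both comparators at the same assumed rate and the allograft arm at twice that rate.

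**Test.** For observed proportions p_i and overall proportion p, X² = Σ n_i(p_i − p)² / [p(1 − p)] on 2 df, rejecting at 5.99 or above. Power is the summed binomial probability of every possible 140/40/40 table that rejects. The miss rate is 1 minus power.

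| Comparators to allograft (assumed) | Power, chi-square | Missed |
|---|---|---|
| 2% to 4% | 1.4% | about 99% |
| 5% to 10% | 12.0% (Fisher 12.4%) | about 88% |
| 10% to 20% | 35.2% | about 65% |
| 20% to 40% | 80.0% | 20% |
| 25% to 50% | 92.4% | about 8% |

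Larger ratios are easier to detect: 15% against 5% is missed about 52% of the time (power 48.1%), and 20% against 5% about 18% (power 82.0%).

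**Does the three-group reading matter?** SAP 9.2 does not call the safety test three-group. That is the natural reading of a comparison by treatment group with no pairwise step. If it is read as allograft against saline alone, 5% to 10% has power of 11.4% (chi-square) or 10.0% (Fisher), so 89% to 90% is missed.

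**Crossover.** If half the conservative-care arm crossed over (assumed), the as-treated groups would be 160/40/20. Power for 5% to 10% would then be 6.8% to 7.6%, so 92% to 93% is missed.

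**What an interval adds.** Suppose SAEs occur in 14/140, 2/40 and 2/40.
- Overall proportion: 18/220 = 0.0818.
- X² = [140(0.100 − 0.0818)² + 80(0.050 − 0.0818)²] / (0.0818 × 0.9182) = 1.69. Chi-square p = 0.43; Fisher exact p = 0.59.
- Allograft minus saline: 10.0% − 5.0% = +5.0 points.
- Wilson 95% limits: 6.05% to 16.09% (14/140) and 1.38% to 16.50% (2/40).
- Newcombe lower limit: 5.0 − √[(10.0 − 6.05)² + (16.50 − 5.0)²] = 5.0 − 12.2 = −7.2.
- Newcombe upper limit: 5.0 + √[(16.09 − 10.0)² + (5.0 − 1.38)²] = 5.0 + 7.1 = +12.1.

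The test reports no significant difference, while the interval shows that an excess of about 12 points is not excluded. Likewise, zero events among 140 allograft patients would leave an exact upper limit of 1 − 0.025^(1/140) = 2.6%.

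**The case against.** The strongest reply is that the plan draws no conclusion from this test. Safety rates are secondary and exploratory, trial success rests on ODI and VASPI alone (SAP 9.1), and Protocol 9.3 assesses safety by incidence and severity of AEs. By-arm percentages are themselves comparative output, and a reader can subtract them. All of this stands. A reader might infer that the plan treats p > 0.05 as proof of safety, or that a p-value is its only comparative output; the documents support neither. What remains is that the interval is missing, and a reader cannot get that by subtraction.

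Second, low power depends on the event. SAP 9.2 covers overall AE rates as well, and if those are 20% or more in the comparators the test detects a doubling at least 80% of the time. This also stands, so the concern is confined to uncommon events.

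Third, a reader might conclude that allograft against saline should replace the three-group test as the single safety comparison. That goes too far. Saline patients also receive a disc injection (Protocol 6.4), so this contrast removes procedural harm, and Protocol 12 says the documented risks are those of the procedures. If both injected arms had a 20% rate against 5% in conservative care (assumed), the three-group test would reject about 56% of the time, and allograft against saline only about 5%. The saline contrast also has less power than the three-group test in the example scenarios. Both contrasts are needed.

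**Conclusion.** The point holds as a gap in estimation. Safety is part of the primary objective, and the plan compares the arms by counts, percentages and an exploratory test, without a risk difference or a confidence interval. The miss rates of about 99%, 88%, 65% and 20% are conditional on the assumed doublings, on equal risk in both comparators and on full arms of 140/40/40. The 88% figure should not be quoted without its assumed rates of 5% and 10%. For uncommon events such as SAEs and re-operations a non-significant result would carry little information; for a doubling of a common AE the test is adequate. No planned decision rule is affected, and intervals cannot make up for a small comparator arm. Severity is minor to moderate.

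**What to change.** In SAP 9.2 and 10, for any AE, SAE, related AE, hospitalisation and re-operation:

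- Report each arm's rate with an exact 95% CI.
- Report risk differences with 95% CIs (Newcombe or exact) for allograft minus saline, labelled as the product effect, and allograft minus conservative care, labelled as product plus injection.
- Give the conservative-care contrast both as randomised and as treated. Label the as-treated version non-randomised with unequal exposure time, because crossover is possible after month 3 (Protocol 7.1.4) and SAP 6.4 groups by treatment received.
- Keep the chi-square or Fisher p-value as descriptive, state that non-significance is not evidence of safety, and word the safety conclusion from the interval limits.
- State which analysis set applies. SAP 6.4 uses the as-treated safety population for adverse events, SAP 9 analyses secondary variables in mITT and PP, and SAP 13 names mITT as primary for safety too.

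The cost is SAP wording and a few table columns, with no new patients or data. The downside is that with 40 patients per comparator the intervals will be wide, so the safety statement will read less favourably than one of no significant difference.
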